### 1.3 Risk-Benefit Assessment

The Sponsor has performed 28-day Good Laboratory Practice (GLP) repeated dose toxicology studies in rats and dogs with results supporting the initiation of the clinical program.

In the first-in-human (FIH) study (GS-1001), the target enzyme, mPGES-1, was fully inhibited at low doses and a dose dependent increased excretion of prostacyclin metabolites was observed in the urine. Thus, the subjects assigned to the GS-248 treatment group in this study may have potential medical benefit on RP from their participation.

In the GS-1001 study GS-248 was administered as an oral solution in single ascending doses (1 mg to 300 mg) and in multiple ascending doses (MAD) (20 mg to 180 mg once daily for 10 days) to healthy volunteers was safe and well tolerated. There was no obvious trend in terms of adverse event (AE) reporting frequency with increasing dose of GS-248 and there was no difference in reporting frequency between subjects who received active treatment and those who received placebo except with regards to gastrointestinal disorders, which were more frequently reported by subjects receiving GS-248 in the MAD part of the study. However, there was no consistent pattern and no apparent dose dependency of gastrointestinal disorders, and a majority of the events were of mild intensity and no event was reported as severe.

The second study in healthy volunteers (GS-1002) evaluated the pharmacokinetic (PK) properties of GS-248 120 mg in single doses using a lipid-based and a dry powder-based formulation in capsule, including food interaction, in healthy volunteers. The number of AEs were low, and GS-248 was considered safe and well tolerated. The lipid-based formulation was selected for this study.

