## 6.2 Safety Assessments

### 6.2.1 Adverse Events

#### 6.2.1.1 Definitions

Per ICH, an AE is defined as any untoward medical occurrence in a subject or clinical investigation subject administered a pharmaceutical product and which does not necessarily have a causal relationship with this treatment. An AE can therefore be any unfavourable or unintended sign (including an abnormal laboratory finding), symptom, or disease temporally associated with the use of a medicinal (investigational) product, whether or not related to the medicinal (investigational) product. The AE may be any of the following:

- A new illness
- An exacerbation of a sign or symptom of the underlying condition or of a concomitant illness
- Unrelated to participation in the clinical study or an effect of the study medication or comparator drug
- A combination of 1 or more of the above factors

No causal relationship with the study medication is implied by the use of the term adverse event.

Planned or elective surgical or invasive procedures for pre-existing conditions that have not worsened are not AEs. However, any complication that occurs during a planned or elective surgery is an AE. Conditions leading to unplanned surgical procedures may be AEs.

When an AE occurs after written consent has been obtained but before the first dose of IMP, the AE will be considered a non-treatment emergent AE. An AE that occurs from the time the subject receives his/her first dose of IMP until his/her last study visit will be considered a treatment-emergent AE regardless of the assessed relationship to the administration of the IMP.

For the recording of pregnancy and relevant laboratory data see [Section 6.2.1.2](#).

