**Severity of Adverse Event:**

Refers to the extent to which an AE affects the subject’s daily activities. Severity will be categorised according to the following criteria:

Mild:	The AE does not interfere with the subject’s routine activities.
Moderate:	The AE interferes with the subject’s daily routine, but usual routine activities can still be carried out.
Severe:	The AE results in the inability to perform routine activities.

The term "severity" is used to describe the intensity of an event. This is not the same as "serious". Seriousness, not severity, serves as the guide for defining regulatory reporting obligations. The highest severity grade attained should be reported, for AEs with divergent severities.

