**Causality of Adverse Event:**

The Investigator must assess the causal relationship between an AE and the IMP using the definitions below and record it the AE Log of the eCRF. An AE is considered causally related to the use of the IMP when the causality assessment is probable or possible.

Probable:	The event has a strong temporal relationship to the IMP or recurs on re-challenge, and another aetiology is unlikely or significantly less likely.
Possible:	The event has a suggestive temporal relationship to the IMP, and an alternative aetiology is equally or less likely.
Unlikely:	The event has no temporal relationship to the IMP or is due to underlying/concurrent illness or effect of another drug (that is, there is no causal relationship between the IMP and the event).

*6.2.1.2 Recording Adverse Events*

All SAEs will be collected from the signing of the informed consent form (ICF) until the follow-up visit at the time points specified in the Overall Schedule of Assessments (SoA) (see [APPENDIX 2](#)).

All AE will be collected from the signing of the ICF until the follow-up visit at the time points specified in the SoA.

**Period: Subject Enrolment to the First Administration of IMP:** Non-treatment emergent AEs will be recorded from the time when the subject is enrolled into the study (date of signature of the informed consent) until first administration of IMP.

**Period: First Administration of IMP to Subject's last study visit:** Thereafter all AEs are treatment-emergent AEs (TEAEs, see Definitions, [Section 6.2.1.1](#)) and will be recorded until the final follow-up visit has been performed.

**Period after last study visit:** Any SAE occurring after the subject's last study visit but considered by the investigator to be related to the IMP will be recorded.

If an AE (serious or not) started during the study but did not end before the final follow-up visit, the investigator should make a reasonable effort to establish the outcome and the end date. If this is not possible, the outcome recorded at the final follow-up visit will be assumed to be the final outcome.

If an event stops and later restarts, all the occurrences must be reported. AEs assessed as related to study medication by the investigator and all SAEs must be followed up until resolution.

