8.1 Adverse events

All AEs occurring during the course of the study will be coded using the latest MedDRA coding dictionary at the time of DBL. All AEs (serious and non-serious) reported from the first day of study treatment up until and including 7 days after the last dose of study treatment will be considered treatment emergent AEs (TEAEs).

Where dates are missing or partially missing, AEs will be assumed to be treatment-emergent, unless there is clear evidence (through comparison of partial dates) to suggest that the AE started prior to the first dose of study treatment or more than 7 days after the last dose of study treatment.

Verbatim terms will be coded by Ergomed and all relevant codes will be stored in the database. It is assumed that for each change in intensity, relationship or seriousness of an AE a new entry of the AE was recorded in the data capture database; hence such cases will be analysed like different phases of the same AE.

Subjects experiencing more than one AE within a given SOC category will be counted only once when calculating the number and percentage of subjects experiencing that SOC (e.g., a subject that experiences both nausea and vomiting will only be counted once in such calculations for the SOC gastrointestinal disorders). Similarly, subjects experiencing the same AE

Statistical Analysis Plan	Version 2.0		Page 26 of 27
Sponsor	Gesynta Pharma AB	Protocol No	GS-2001

multiple times throughout the course of the trial will be counted only once when calculating the number and percentage of subjects experiencing that PT (e.g., a subject that experiences mild nausea in both the first and fourth treatment cycle will only be counted once in such calculations for mild nausea). If a PT is reported at more than one severity level for a given subject, the greatest severity will be presented in the summary table.

If the same PT is reported multiple times for a given subject, but with varying study drug relationship assignment, the worst-case attribution will be presented in the summary table.

An AE is considered drug-related if the relationship to study drug is classified as either ‘Possible’ or ‘Probable’.

The following AE summaries will be provided:

- An AE overview table will be created displaying the number of TEAEs, number/percentage of subjects experiencing any TEAE, deaths, any SAE, any TEAEs causing discontinuation, any severe TEAE and any drug-related TEAE per treatment group.

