- A summary of the number of events (TEAEs) by treatment group, SOC and PT
- A summary of the number and percentage of subjects reporting a TEAE by treatment group, SOC and PT
- A summary of the number of TEAEs by treatment group, intensity and PT
- A summary of the number and percentage of subjects reporting a TEAE by treatment group, intensity and PT
- A summary of the number and percentage of subjects reporting a TEAE by treatment group, relationship and PT
- A summary of the number of subjects reporting a TEAE with a frequency of $\geq 2\%$ by treatment group and PT
- A summary of the number and percentage of subjects reporting a non-serious adverse event occurring in greater than 5% of subjects by treatment group, SOC and PT

TEAE summaries will be ordered in terms of international order of SOC, and alphabetically for PT within SOC.

For the summary of TEAE with a frequency of $\geq 2\%$ TEAEs will be ordered by decreasing frequency.

For each subject and each AE, the worst intensity recorded will be attributed and used in the by-intensity summaries. Similarly, the worst relationship will be attributed and used in the by-relationship summaries.

All adverse events (i.e. TEAEs as well as non-treatment emergent events) will be listed in section 16.2 of the CSR. However, only TEAEs will be summarized in the tables.

AE listings will be presented by treatment group and will include: subject identifier, treatment, age, sex, race, AE (PT and verbatim term), study day of onset, duration, intensity, seriousness, action taken, relationship, outcome and concomitant medication given (including CM number).

Statistical Analysis Plan	Version 2.0		Page 27 of 28
Sponsor	Gesynta Pharma AB	Protocol No	GS-2001

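### Neither definition of a treatment-emergent AE covers an event that starts before first dose and worsens on treatment, and the SAP relies on split entries that the protocol does not ask for

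*SAP*

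**What the plan says.** **Collection.** Protocol 6.2.1.2: "All AE will be collected from the signing of the ICF until the follow-up visit". Screening is at Day -21 to -14 (protocol 7.1.1), so every subject has a pre-dose period in which an AE can start.

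**Severity and repeat entries.** The severity paragraph of protocol 6.2.1.1 says: "The highest severity grade attained should be reported, for AEs with divergent severities". Protocol 6.2.1.2 says: "If an event stops and later restarts, all the occurrences must be reported". The protocol has no instruction to make a new entry when a continuing AE changes in intensity, relationship or seriousness.

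**Treatment-emergent status.** Under protocol 6.2.1.1, when an AE occurs after consent but "before the first dose of IMP, the AE will be considered a non-treatment emergent AE". SAP 8.1 counts as TEAEs those AEs "reported from the first day of study treatment up until and including 7 days after the last dose of study treatment". Neither text mentions worsening after first dose.

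**Data structure assumed in the SAP.** SAP 8.1: "It is assumed that for each change in intensity, relationship or seriousness of an AE a new entry of the AE was recorded". It then handles such entries as phases of a single AE.

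**What is tabulated.** SAP 8.1 lists all AEs, then adds: "However, only TEAEs will be summarized in the tables". SAP 8.2 opens by stating that its summary tables include TEAEs.

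**The concern.** The SAP and the protocol describe different AE records. The SAP expects a worsening to arrive as its own entry. The protocol's severity rule is most naturally met by one entry carrying the highest grade reached. With no worsening clause in either TEAE definition, the table in which a worsening is counted depends on how each site chose to enter it.

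Safety is part of the primary objective, and AE incidence is the first safety endpoint in protocol Table 2.1. An AE that is mild in run-in and more severe on study drug is one that a safety summary should show. If it is held as one record with a run-in onset, the tables omit it. Depending on the case, that can affect the rows for any TEAE, severe TEAEs, drug-related TEAEs and TEAEs causing discontinuation. The listing does not repair this. Its fields in SAP 8.1 include onset day, duration and intensity but no date of worsening, so the event would read as severe with a pre-dose onset and the reader could not tell when it became severe.

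**Working it through.** The plan gives no figure on this point, so the check is a comparison of texts followed by one traced event.

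**Step 1. Is the SAP's assumption backed by an instruction to sites?** SAP 8.1 assumes a new entry per change. Protocol 6.2.1.1 fixes which grade to report, and protocol 6.2.1.2 requires repeat reporting for events that stop and restart. Neither tells sites to split a continuing AE. The eCRF completion guidelines mentioned in protocol 6.2.1.3 might do so, but they are not among the documents.

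**Step 2. Is TEAE status decided by onset?** The protocol ties it to when the AE occurs relative to first dose. The SAP sentence uses the word reported, which is ambiguous. Its rule for missing dates, however, asks whether the AE started before first dose or more than 7 days after the last dose. The working test is therefore onset.

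**Step 3. Trace one AE (illustrative dates).** Mild from Day -5, severe from Day 10, last dose on Day 28. The SAP window runs from Day 1 to Day 28 + 7 = Day 35.

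| Recording | Date tested | In Day 1 to 35? | Result |
|---|---|---|---|
| One record at highest grade | Day -5 | No | 0 rows in the TEAE tables, 1 row in the listing, shown as severe |
| Two entries, as the SAP assumes | Day 10 | Yes | 1 subject counted, severe |

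The second result holds if the Day 10 entry is judged by its own date. The SAP calls such entries phases of the same AE and does not say whether a later phase keeps the original onset. If it does, split entries lose the worsening too.

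**Step 4. Weight of one subject.** Protocol 3.1 plans about 40 per arm.

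- 1/40 = 2.5%. If the SAP's 2% threshold is applied per arm, one subject can decide whether a preferred term appears in that table. Over both arms it would be 1/80 = 1.25%, below the threshold.
- For the table of non-serious events above 5%, applied per arm, 2/40 = 5.0% does not exceed the limit and 3/40 = 7.5% does.

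**Step 5. Number of subjects affected.** This needs the share of subjects with an AE open at first dose, and the share of those who worsen on treatment. The documents give neither.

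**The case against.** **The protocol does not forbid a second entry.** The severity rule says which grade to report. It says nothing about records and does not address an AE that spans first dose. The SAP sentence may describe correctly how the database was filled. This stands. A reader might infer that every such AE stays a single pre-dose record; the documents show only that nothing in the protocol tells sites to split it.

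**There are routes for recording a worsening as a new AE.** Protocol 6.2.1.1 counts an exacerbation of the underlying condition or of a concomitant illness as an AE. Protocol 6.2.1.2 does so for a clinically relevant laboratory change from pre-treatment. Protocol 6.2.8 sends an adverse change from the Day 1 examination to the AE page. These routes are real but partial. The laboratory route closes when the value is a sign of an AE already recorded, and none clearly covers worsening of an open symptom such as nausea.

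**Not every table is affected.** A reader might infer that the worsening vanishes from all AE tables. In the SAP, the overview items for deaths and any SAE, and the COVID-19 summary, are not themselves worded as TEAE-only, although the general sentences may restrict them. Missing or partial dates default to treatment-emergent unless there is clear evidence otherwise. All AEs remain listed, and SAP 8.2 provides detailed listings of serious events, with narratives in the study report. This stands.

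**Size and direction.** A reader might put a percentage on the loss or conclude that the tables favour GS-248. The documents support neither. A subject leaves the any-TEAE row only if no other TEAE is recorded, and leaves the severe row only if the worsening reached severe. Natural worsening is lost on placebo as well, so the arm difference is distorted only as far as worsening rates differ between arms. The protocol does report "gastrointestinal disorders, which were more frequently reported by subjects receiving GS-248 in the MAD part of the study", but the same paragraph finds no consistent pattern, no apparent dose dependency, mostly mild events and none severe. It does not describe worsening of existing symptoms.

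**Conclusion.** The point holds as a gap in the TEAE rule combined with an unsupported assumption about the data. Neither definition covers an AE that starts before first dose and worsens on treatment, and the split entries that would close the gap are not instructed anywhere in the protocol.

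The loss is conditional. It requires that the AE is kept as one record, that status is decided by onset, and that the pre-dose onset date is known. Where all three apply, the worsening is missing from the TEAE tables and only the listings remain. Each affected subject is worth up to 2.5 percentage points in any one row of an arm of about 40. The total number and the net effect on the comparison between arms cannot be stated from the documents.

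This is more than a missing detail, because a stated rule can misclassify on-treatment worsening in an endpoint that belongs to the primary objective. It can be corrected before unblinding at little cost.

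**What to change.** 1. **TEAE definition.** In SAP 8.1, and for consistency in protocol 6.2.1.1, define a TEAE as an AE that starts on or after first dose within the TEAE window, or that started before first dose and increases in intensity or becomes serious on or after first dose within that window.
2. **Recording rule.** Replace the SAP's assumption sentence with one rule that is reconciled with the protocol's highest-grade instruction: for an AE open at first dose, either a separate dated entry or a recorded date of worsening. State that the date of worsening decides treatment-emergent status, so that a later phase does not inherit the run-in onset.
3. **Data check.** Before unblinding, query every AE with pre-dose onset still ongoing on Day 1 for a date of worsening. The SAP is at version 2.0 and already reports blinded diary review, so for records already entered this query does most of the work.

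**Cost.** Wording changes, a small query run for the sites, and slightly higher TEAE counts in both arms.

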8.2 Deaths, serious adverse events and other significant adverse events

TEAEs will be included in the summary tables below.

The following AE summaries will be provided on deaths, SAEs and other significant adverse events:

- A summary of the number and percentage of subjects reporting a TEAE with outcome of death by treatment group, SOC and PT
- A summary of key subject information for subjects reporting TEAE with outcome of death
- A summary of the number of SAEs reported by treatment group, SOC and PT
- A summary of the number and percentage of subjects reporting a SAE by treatment group, SOC and PT
- A summary of key subject information for subjects reporting a SAE
- A listing and summary of subjects reporting COVID-19 infection as recorded as an AE

Detailed listings of all fatal and other serious events will be provided (for section 14.3.2). Narratives will not be included in section 14.3.3 but will be provided by medical writing in section 12.3.2 of the CSR.

8.3 Vital signs

For the vital signs safety analysis, data from Visit 2 onwards will be used only.

Vital signs parameters (systolic/diastolic blood pressure, heart rate, body weight) will be assessed at each of the visits as per schedule of assessment.

The following summaries will be provided:

- A summary of the observed absolute values and change from baseline in each vital sign parameter by treatment group and time point.

Any clinically relevant vital signs measurement was to be recorded as an AE and will be presented with the AEs.

By-subject listings of vital signs (including screening data) will also be provided.

8.4 ECG

ECGs are scheduled at the following visits/time-points:

Visit/Time	ECG schedule
Visit 1/Screening	Triple ECG ECG result summary

Statistical Analysis Plan	Version 2.0		Page 28 of 29
Sponsor	Gesyntha Pharma AB	Protocol No	GS-2001

Visit 2/Day 1, prior to dosing	Triple ECG ECG result summary
Visit 2/Day 1, 170 min post-IMP administration	Triple ECG ECG result summary
Visit 3/Day 15	Triple ECG ECG result summary
Visit 5/Follow-up (and/or early termination)	Triple ECG ECG result summary

For the ECG safety analysis, data from Visit 2 onwards will be used only.

The following ECG parameters are captured:

- RR interval
- PR interval
- QRS interval
- QT interval
- QTc interval
- QTcF interval
- Mean QTcF interval
- ECG normality/abnormality evaluation

8.4.1 Descriptive statistics

The triple ECG parameter results will be averaged per assessment (visit 2 (pre-dose, baseline), visit 2 (170 min post dose), 3 and 5).

For the derivation of change from baseline, the mean of the triple ECG pre-dose measurement on visit 2/Day 1 will be used as the baseline value.

The following summaries will be provided:

- Descriptive statistics of the mean absolute values and change from baseline of the mean values for each ECG parameter by treatment group and time point for visit 2 (pre-dose, baseline), visit 2 (post-dose), visit 3 and visit 5.

8.4.2 QTc prolongation

Evaluation of QTc prolongation will be based on the mean QTcF interval parameter as captured in the eCRF.

QTcF Frequencies will be calculated for following classified values and changes (according to ICH E14):

- Absolute values: ≤ 450 ms as normal, $>450-480$ ms, $>480-500$ ms, >500 ms
- Changes from baseline: decreases or increases ≤ 30 as normal, increases $>30-60$ ms, increases >60 ms.

Statistical Analysis Plan	Version 2.0		Page 29 of 30
Sponsor	Gesyntha Pharma AB	Protocol No	GS-2001

8.4.3 ECG categorical data

For the evaluation of ECG categorical data the result at the visit 2, pre-dose will be used as the baseline value.

The 12-lead ECG categorical data, will be summarized by treatment group using a shift table from baseline to each subsequent assessment time point and categories of normal, abnormal NCS, and abnormal CS.

8.4.4 Listings

Screening ECG data will be included in the listings only.

By-subject listings of ECG results (original, mean of triple measurements and ECG abnormalities) will be provided.

8.5 Laboratory variables

The following routine laboratory safety data are collected through the Central Laboratory:

Clinical chemistry	Haematology	Urinalysis
Albumin	Haemoglobin	pH
Sodium	Erythrocyte count	Glucose
Potassium	Ery-Mean Corpuscular Volume	Ketone
Calcium, total	Haematocrit (Erythrocyte volume fraction)	Bilirubin
Glucose	Platelet count (Thrombocyte particle concentration)	Blood
C-reactive protein (P-CRP)	Leukocyte count (LPC)	Creatinine
Bilirubin, total	Leukocyte differential, absolute count (lymphocytes, monocytes, neutrophil-, eosinophil- and basophil- granulocytes)	WOCBP pregnancy test
Bilirubin - conjugated		Drug screen
Uric acid		
ASAT		
ALAT		
Cholesterol		
Cystatin C		
Creatinine		
eGFR		
Osmolality		
Urea or BUN		
ALP		
GT		
LDH		
Electrophoresis		
pro-BNP		

For the safety laboratory analysis, data from Visit 2 onwards will be used only.

8.5.1 Continuous laboratory data:

- Continuous data laboratory safety data (original values and change from baseline) will be summarized using descriptive statistics per visit and treatment group.
- Frequencies of high and low values with respect to the normal range will be displayed by visit and treatment group
- Shift tables comparing each post-baseline visit with baseline with respect to normal range will be displayed by treatment group.

Statistical Analysis Plan	Version 2.0		Page 30 of 31
Sponsor	Gesyntha Pharma AB	Protocol No	GS-2001

- In addition, abnormal values outside reference ranges will be summarized in a listing per visit and per subject.

8.5.2 Qualitative laboratory data:

For qualitative laboratory safety data ordered frequency tables will be prepared per visit and treatment group.

Frequencies of shift comparing each post-baseline visit with baseline will be displayed by treatment group.

